2.1.1 Secondary Objectives and Associated Endpoints

Table 2 Secondary Objectives and Associated Endpoints

Type	Objective	Endpoint
PK	To evaluate serum concentrations of MEDI8897 and palivizumab	
 MEDI8897 and palivizumab serum concentrations MEDI8897 and palivizumab PK parameters: Summary of serum concentrations and estimated PK parameters (C_{max}, AUC, apparent clearance, and $t_{1/2}$, if data permit)
ADA	To evaluate ADA responses to MEDI8897 and to palivizumab in serum	Incidence of ADA to MEDI8897 and palivizumab in serum
Efficacy	To assess the descriptive efficacy of MEDI8897 when administered as a single IM dose of 50 mg to infants < 5 kg or 100 mg to infants \geq 5 kg in the first RSV season or a single 200-mg IM dose	
 Incidence of medically attended LRTI (inpatient and outpatient) due to RT-PCR-confirmed RSV through 150 days after Dose 1 for Season 1 and Season 2

Table 2 Secondary Objectives and Associated Endpoints

Type	Objective	Endpoint
	administered in the second RSV season, in reducing medically attended LRTI (inpatient and outpatient) and hospitalization due to RT-PCR-confirmed RSV, compared to palivizumab	
 Incidence of hospitalizations due to RT-PCR-confirmed RSV through 150 days after Dose 1 for Season 1 and Season 2

ADA = anti-drug antibody; AUC = area under the concentration-time curve; C_{max} = maximum observed concentration; IM = intramuscular; LRTI = lower respiratory tract infection; PK = pharmacokinetic; RSV = respiratory syncytial virus; RT-PCR = reverse transcriptase-polymerase chain reaction; $t_{1/2}$ = terminal half-life.

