4.3 Description of Study Procedures

4.3.1 Efficacy

4.3.1.1 Lower Respiratory Tract Infection

Subjects will be monitored throughout the study for LRTI (see [Table 5](#) and [Table 6](#)). All subjects seeking medical attention for a respiratory illness (in either the inpatient or outpatient setting) will be evaluated for LRTI. All subjects found to have an LRTI and all subjects who require hospitalization for a respiratory infection, even if there is not a diagnosis of LRTI, should have respiratory samples obtained and respiratory assessment forms completed. Samples should be collected for all of these respiratory events even those not meeting the protocol definition of LRTI. Subjects who have a primary hospitalization for a respiratory infection (ie, upper or lower tract) or a respiratory deterioration during a hospitalization, or who seek outpatient medical attention (including ER visits) for a lower respiratory illness, will be assessed clinically for the presence of LRTI and for RSV by central laboratory diagnostic testing of respiratory secretions. Testing for RSV will be performed using the US FDA-cleared and CE-marked in vitro diagnostic real-time RT-PCR assay (Lyra RSV + human metapneumovirus [hMPV] assay; Quidel Corporation, San Diego, CA, www.quidel.com; see [Section 4.3.1.2](#)). A diagnosis of RSV LRTI requires having a respiratory sample positive for RSV by the central laboratory RT-PCR assay.

In addition to the clinical assessment of LRTI, there is a protocol definition using objective criteria for the determination of a medically attended protocol-defined LRTI.

For subjects with no underlying lung disease:

To meet the protocol-defined endpoint of medically attended RSV LRTI, subjects with signs of LRTI must have documented at least one physical examination finding of rhonchi, rales, crackles, or wheeze AND at least one of the following clinical signs (see [Table 7](#)):

- Increased respiratory rate at rest (age: < 2 months, ≥ 60 breaths/min; 2 to 6 months, ≥ 50 breaths/min; > 6 months, ≥ 40 breaths/min), OR
- Hypoxemia (in room air: oxygen saturation < 95% at altitudes $\leq 1,800$ meters or < 92% at altitudes > 1,800 meters), OR
- Clinical signs of severe respiratory disease (eg, acute hypoxic or ventilatory failure, new onset apnea, nasal flaring, intercostal, subcostal or supraclavicular retractions, grunting) or dehydration secondary to inadequate oral intake due to respiratory distress (need for intravenous fluid).

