
RSV Confirmed:
 
 Positive by central laboratory real-time RT-PCR assay 	
Documented new or worsened physical examination findings localizing to lower respiratory tract:
 
 Rhonchi Rales Crackles Wheeze 	
Objective measures of clinical severity:
 
 Increased respiratory rate (from baseline) Hypoxemia Acute hypoxic or ventilatory failure New onset apnea Nasal flaring Retractions Grunting Dehydration due to respiratory distress Prescription of new or increased (from baseline) dose of medications including bronchodilators, steroids, diuretics, cardiac medication

CHD = congenital heart disease; CLD = chronic lung disease; LRTI = lower respiratory tract infection; PE = physical examination; RSV = respiratory syncytial virus; RT-PCR = reverse transcriptase-polymerase chain reaction.

Note: One item from each column is required to meet the protocol-defined endpoint of medically attended RSV LRTI.

RSV Hospitalization

An RSV hospitalization is defined as either (1) a respiratory hospitalization with a positive RSV test within approximately 2 days of hospital admission (primary) or (2) a new onset of respiratory symptoms in an already hospitalized subject, with an objective measure of worsening respiratory status and positive RSV test (nosocomial). Primary and nosocomial RSV hospitalization are further defined below.

Primary RSV Hospitalization

RSV diagnostic testing will be performed on respiratory secretions obtained within approximately 2 days before or after admission for subjects hospitalized for any respiratory infection (upper or lower respiratory tract). If the RSV diagnostic test (performed centrally via RT-PCR) is positive, the hospitalization will be classified as a primary RSV hospitalization. Deaths that can be demonstrated as caused by RSV (by autopsy or clinical history and virologic evidence) will also be considered as primary RSV hospitalization endpoints.

Nosocomial RSV Hospitalization

Subjects hospitalized for a respiratory illness or non-respiratory illness whose RSV diagnostic test is negative may develop nosocomial RSV illness during the study.

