3.5.1 Incidence of medically attended LRTI due to RT-PCR-confirmed RSV

The determination of medically attended RSV LRTI will be based on objective clinical LRTI criteria (described in the Protocol Section 4.3.1.1 and SAP Appendix 1) and RSV test results obtained from analyzing the respiratory secretions using a validated RSV RT-PCR assay for the detection of RSV A or RSV B performed in a central laboratory. These LRTI events may occur in the inpatient or outpatient visit setting.

Based on a blinded review of data, it is determined that a medically attended LRTI will be counted as a medically attended RSV LRTI if there is a respiratory sample tested RSV positive and collected within [-7, 14] days relative to the initial date seen by the healthcare provider (eg, admission/deterioration date associated with the event, urgent care visit, outpatient emergency department [ED] visit, or outpatient clinic visit). In addition, deaths that can be demonstrated as caused by RSV (by autopsy or clinical history and virologic evidence) will also be considered as primary medically attended RSV LRTI events.

3.5.1.1 Analysis of incidence of medically attended LRTI due to RT-PCR-confirmed RSV in Season 1

The incidence of medically attended RSV LRTI (inpatient and outpatient) through 150 days post 1st dose (ie, during a typical 5-month RSV season) in Season 1 is the primary efficacy endpoint and will be summarized by treatment group as well as for all subjects using ITT

population. The 95% Clopper-Pearson (exact) confidence interval of the incidence rate for each treatment group will be produced using the SAS Procedure PROC FREQ with the EXACT statement. For subjects with multiple medically attended RSV LRTI events, only the first occurrence will be used in the summary. Summary of the incidence of medically attended RSV LRTI will also be repeated for CHD subjects and CLD subjects separately.

In addition, the incidence of medically attended RSV LRTI will be further tabulated by Inpatient (primary hospitalization, nosocomial hospitalization) and Outpatient, for the latter category, further presentation will be made by different medical settings: outpatient clinic, urgent care clinic, and ED visits for subjects who did not have a hospitalization due to RSV.

The incidence of medically attended RSV LRTI will also be summarized by the following subgroups:

- Hemisphere
- Age at randomization stratum (age \leq 3.0 months, age > 3.0 to \leq 6.0 months, age > 6.0 months)

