3.5.2 Incidence of RSV hospitalization

The events of "RSV hospitalization" are a subset of "medically attended RSV LRTI," which are determined based on objective clinical LRTI criteria (described in the Protocol Section 4.3.1.1 and SAP Appendix 1) and RSV test results obtained from central laboratory analysis respiratory secretions using a validated RSV RT-PCR assay for the detection of RSV A or RSV B.

3.5.2.1 Analysis of Incidence of RSV hospitalization in Season 1

The incidence of RSV hospitalization through 150 days after dosing in Season 1 (ie, during the 5-month RSV season) will be summarized by treatment group for each cohort as well as for all subjects. For subjects with multiple RSV LRTI hospitalizations, only the first occurrence will be used in the analysis.

For each treatment group, age at onset of the first medically attended RSV LRTI hospitalization will be tabulated by age group used for randomization stratification by treatment group. In addition, time-to-first medically attended RSV LRTI hospitalization will be plotted at subject's level along the axis of age at birth. RSV LRTI hospitalization will also be summarized by RSV subtype (A or B). The incidence of RSV LRTI hospitalization will also be summarized by the following subgroups.

- Hemisphere
- Age at randomization stratum (age \leq 3.0 months, age > 3.0 to \leq 6.0 months, age > 6.0 months)
- Gender
- Race (Caucasian, non-Caucasian)
- Weight at birth (weight ≤ 2.5 kg, weight ≥ 2.5 kg)
- Weight on Day 1 (weight $\leq 5 \text{ kg}$, weight $\geq 5 \text{ kg}$)
- GA (< 29 weeks, ≥ 29 weeks to < 32 weeks, ≥ 32 weeks to < 35 weeks, ≥ 35 weeks)
- Sibling also participating in the study (yes/no)

Above summaries will be repeated for each cohort (preterm and CHD/CLD).

3.5.2.2 Analysis of Incidence of RSV hospitalization in Season 2

The efficacy summary in Season 2 (ie, Day 1, Season 2 through Day 361, Season 2) will focus on the CHD/CLD subjects who have been randomized to palivizumab group in Season 1 and enrolled (re-randomized) in Season 2 in either palivizumab or MEDI8897 groups (ie, palivizumab/palivizumab and palivizumab/MEDI8897 groups), to facilitate understanding the effects of MEDI8897 and palivizumab following an initial treatment by palivizumab in the first RSV season. Efficacy data of CHD/CLD subjects who have been randomized to

MEDI8897 group in both Season 1 and Season 2 (ie, MEDI8897/MEDI8897 group) will also be summarized.

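### SAP 3.5.2 requires the LRTI criteria for RSV hospitalization, which Protocol 4.3.1.1 does not, so one secondary endpoint has two definitions under one label

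*SAP*

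**What the plan says.** Protocol 2.1.1 lists RSV hospitalization as a secondary endpoint in its own right, separate from medically attended RSV LRTI: "Incidence of hospitalizations due to RT-PCR-confirmed RSV through 150 days after Dose 1 for Season 1 and Season 2".

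Protocol 4.3.1.1 defines it. For a primary event, respiratory secretions are "obtained within approximately 2 days before or after admission for subjects hospitalized for any respiratory infection (upper or lower respiratory tract"), and then: "If the RSV diagnostic test (performed centrally via RT-PCR) is positive, the hospitalization will be classified as a primary RSV hospitalization". Deaths shown to be caused by RSV also count as primary RSV hospitalizations. A nosocomial event is stricter. It needs signs of a new lower respiratory illness, an objective worsening of respiratory status and a positive central test. The same section requires samples from "all subjects who require hospitalization for a respiratory infection, even if there is not a diagnosis of LRTI".

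SAP 3.5 names the endpoint protocol-defined RSV hospitalization and gives 'RSV LRTI hospitalization' as another name for it. SAP 3.5.2 then states that the events "are a subset of 'medically attended RSV LRTI,' which are determined based on objective clinical LRTI criteria", with reference to Protocol 4.3.1.1 and SAP Appendix 1. Those criteria require a positive central RT-PCR, a lower-tract finding on examination (rhonchi, rales, crackles or wheeze) and at least one marker of medical significance.

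Through the subset rule the endpoint also takes on the sample window of SAP 3.5.1, which accepts a "respiratory sample tested RSV positive and collected within [-7, 14] days relative to the initial date" of contact with the healthcare provider.

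**The concern.** The two documents attach the same name to two case definitions. Under the protocol, a child admitted with an RSV-positive upper-tract infection is an endpoint event. So is a child admitted with clinically diagnosed LRTI whose record lacks a qualifying chest finding or severity sign. Under SAP 3.5.2 neither is. Because SAP 3.5 keeps the protocol-defined label, a reader of the study report would take the SAP figure for the protocol endpoint.

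At stake is whether a named secondary endpoint is reported as the protocol defines it. Few events are expected, and Protocol 4.8.2 warns that reduced RSV circulation could make rates much lower still, so a handful of reclassified admissions would be visible in the table.

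**Working it through.** **1. The definitions side by side**

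| Element | Protocol 4.3.1.1 | SAP 3.5.2 |
|---|---|---|
| Primary event: reason for admission | Any respiratory infection, upper or lower | Must be a medically attended RSV LRTI |
| Chest finding | Not required for a primary event | Required |
| Severity sign | Not required for a primary event | Required |
| Central RT-PCR positive | Required | Required |
| Sample timing | About 2 days either side of admission (primary) | Days -7 to +14 (from SAP 3.5.1) |
| Demonstrated RSV death | Counts as a primary RSV hospitalization | Counted as RSV LRTI in SAP 3.5.1; SAP 3.5.2 is silent |

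On clinical criteria the SAP is narrower. On sample timing it is wider. The gap lies mainly in primary admissions, because the protocol already asks for lower respiratory signs in nosocomial events. A nosocomial case whose only such sign is retractions could still fail the SAP's chest-finding requirement.

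**2. Is the difference recorded?** SAP edition 2 is dated 05 April 2021, days after Protocol Amendment 1 (31 March 2021), which keeps the broad definition. The SAP amendment history lists the [-7, 14] window but says nothing about the LRTI restriction on hospitalization.

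**3. Can the protocol endpoint be recovered from SAP 3.5.3?** That section tabulates hospitalizations for any respiratory illness by LRTI or non-LRTI and then by RSV status. Each subject appears once, ranked LRTI above non-LRTI before RSV above non-RSV. Take a child with one admission for non-RSV LRTI and another for RSV-positive upper-tract infection. The protocol counts an event, but the table shows only a non-RSV LRTI. The summary that ignores severity covers LRTI events only. Adding up the RSV-positive cells comes close but is not exact.

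**4. Size**

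Inputs from Protocol 4.8.2: 300 palivizumab and 600 MEDI8897 subjects; a 6% RSV LRTI rate, made up of 1.9% hospitalization and 3.9% outpatient illness.

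- The plan's own figures: 300 × 0.06 = 18 and 600 × 0.06 = 36. Both reproduce. The unrounded sum of 5.8% gives 17.4 and 34.8.
- Hospitalizations: 300 × 0.019 = 5.7; 600 × 0.019 = 11.4; total 17.1.
- One reclassified admission moves the rate by 1/300 = 0.33 percentage points (palivizumab) or 1/600 = 0.17 (MEDI8897).
- For illustration, exact 95% intervals in palivizumab: 6/300 gives 0.74% to 4.30%; 5/300 gives 0.54% to 3.85%; 4/300 gives 0.36% to 3.38%.

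Let f be the share of RSV-positive respiratory admissions that fail the LRTI criteria. The documents give no value for f. They also do not say which definition underlies the 1.9%, which they present as a component of the RSV LRTI rate. With sample timing set aside, the number left out of the SAP endpoint over both arms is:

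- 17.1 × f, if the 1.9% follows the broad definition;
- 17.1 × f / (1 − f), if it is already restricted to LRTI.

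For assumed f of 10%, 20% and 30%, the first gives 1.7, 3.4 and 5.1 and the second 1.9, 4.3 and 7.3. These show sensitivity to an unknown. They are not estimates.

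**The case against.** The case for leaving the SAP alone has four parts.

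- **The admissions stay visible.** SAP 3.5.3 reports them by treatment group on the ITT population through Day 150, after Day 150 and through Day 360. SAP 3.5 also discloses the alternative name. This stands as mitigation. A reader might infer that these events vanish from the report, and the documents do not support that. What remains is that the named endpoint excludes them and cannot be rebuilt exactly.
- **The protocol is not uniform.** Section 3.2.3 speaks of LRTI as including RSV-associated hospitalization, and section 4.8.2 counts hospitalizations inside the LRTI rate. Neither overrides the explicit definition in 4.3.1.1. The similar strategy promised in 4.8.4 concerns how the endpoint is summarized. This does make amending the protocol a legitimate alternative.
- **The SAP endpoint need not be smaller.** Its sample window is wider, so the net direction is unknown. This stands.
- **Nothing inferential depends on it.** The primary objective is safety, efficacy is descriptive, and one rule applies to both arms. This stands and lowers the severity.

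A reader might also infer that the [-7, 14] window turns hospital-acquired RSV into events dated at admission and therefore needs a rule on which swab governs. The documents do not support going that far. The window was set on blinded data, is recorded in the amendment history and is anchored to the admission or deterioration date. The SAP is silent on conflicting swabs, so misdating is possible but is not a stated rule. A precedence rule appears in neither document and would alter the primary efficacy endpoint.

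**Conclusion.** The mismatch is real. It rests on the text of Protocol 4.3.1.1, SAP 3.5 and SAP 3.5.2, with no numerical assumption. RSV-positive respiratory admissions that miss the LRTI criteria count under the protocol but not in the SAP endpoint, and RSV deaths have no stated place in the SAP's hospitalization endpoint.

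The number affected is not derivable. It would be tempting to take a percentage off the 5.7 and 11.4 expected events and call that the loss. That needs both the share f and a 1.9% known to follow the broad definition, and the documents supply neither. What can be said is that about 17 Season 1 hospitalizations are implied by the planning rate, and each one carries weight.

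No test, alpha or power is affected, and no bias between arms follows from a rule applied equally to both. This should be corrected before database lock, but it does not threaten the trial's main conclusion.

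**What to change.** In SAP 3.5.2, analyse RSV hospitalization as Protocol 4.3.1.1 defines it:

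- *Primary:* any respiratory admission, upper or lower tract, with a positive central RT-PCR, and including demonstrated RSV deaths.
- *Nosocomial:* with the lower respiratory signs, objective worsening and positive central test that the protocol requires.

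Keep the present subset as an additional row labelled 'RSV LRTI hospitalization', and reserve the protocol-defined label for the first. State in 3.5.2 which sample window applies. At most, add one sensitivity row for primary RSV hospitalization using the protocol's window of about 2 days. The primary efficacy endpoint in SAP 3.5.1 needs no change.

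Alternatively, amend the protocol definition to the LRTI subset before database lock and record the reason in both documents.

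The cost is a paragraph of SAP text, an amendment-history entry and one or two table rows. No new data are needed: the protocol already requires samples from respiratory admissions without an LRTI diagnosis, and SAP 3.5.3 already classifies these admissions by LRTI and RSV status.

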3.5.3 Other Efficacy Analyses

For each season, the following summaries will be provided using the respective ITT population. The Season 1 summaries will also be repeated for each cohort (preterm, CHD/CLD).

An overall summary of subjects with any medically attended LRTI (protocol-defined or not) or hospitalization due to any respiratory illness will be presented by treatment group. In this summary, a subject is reported only once even though he or she might have multiple events in the time interval of reporting. In that occasion, the event with the highest severity level will be reported. The rules to define severity among multiple LRTI events for a subject are as follows: protocol-defined > non-protocol defined, RSV > non-RSV, and hospitalization > nonhospitalization. The rules to define severity among multiple hospitalizations due to any respiratory illness are as follows: LRTI > non-LRTI, RSV > non-RSV. Incidence of all medically attended LRTI will be summarized by protocol-defined LRTI (RSV or non-RSV) and non-protocol defined LRTI (RSV or non-RSV) with each further breaking down by hospitalization status. For subjects who were hospitalized due to any respiratory illness, LRTI and non-LRTI cases will be further reported and broken down by RSV status. In addition, a summary for subjects with at least one medically attended LRTI event (categorized by RSV, non-RSV, then further by hospitalization, outpatient only), regardless of severity, will be presented. In this summary, a subject can be reported in multiple event categories as long as the subject has at least one corresponding event.

Summaries for subjects who met primary efficacy endpoint (ie, protocol-defined medically attended RSV LRTI) will be presented by treatment group for each of the elements used to evaluate for the case definition of medically attended RSV LRTI (Appendix 1). The summaries for subjects with or without underlying lung disease will be provided separately. The elements include the following:

- For subjects without underlying lung disease: rhonchi, rales, crackles, wheeze, increased respiratory rate, hypoxemia, acute hypoxic or ventilatory failure, new onset apnea, nasal flaring, retractions, grunting, dehydration due to respiratory distress requiring IV hydration
- For subjects with underlying lung disease: rhonchi, rales, crackles, wheeze, increased respiratory rate (from baseline), hypoxemia, acute hypoxic or ventilatory failure, new onset apnea, nasal flaring, retractions, grunting, dehydration due to respiratory distress,

prescription of new or increased (from baseline) dose of medications including bronchodilators, steroids, diuretics, cardiac medication

In this summary, a subject is reported once even though he or she might have the element multiple times during the reporting period.

For all medically attended LRTI events, RSV status (positive, negative or not done) will be summarized by central RT-PCR or local testing results by treatment group. The proportion of each category will be calculated based on the total number of LRTI events for the respective treatment group. In addition, incidence of positive RSV LRTI either by RT-PCR or by local testing results will also be summarized by LRTI categories (protocol-defined, non-protocol defined) and treatment group. The same analysis window as described in above sections for the RT-PCR central tests will be used for the local tests. In this summary, if a subject has multiple LRTI events, the one with the highest severity will be reported (in the order of protocol-defined > non-protocol defined) and the incidence of the event will be calculated based on the number of randomized subjects for the respective treatment group.

In addition, for each treatment group, all medically attended LRTI events will be tabulated by Inpatient (primary hospitalization, nosocomial hospitalization) and Outpatient. For the latter category, further presentation will be made by different medical settings: outpatient clinic, urgent care clinic, and ED visits. The proportion of each category will be calculated based on the total number of LRTI events for the respective treatment group.

All above stated summaries will be presented through 150 days post 1st dose (on ITT population), after 150 days post 1st dose (on the ITT population with Day 151 visit), and through 360 days post 1st dose (on ITT population).

For various LRTI events, including the primary endpoint, detailed definitions of new onset of events are defined in Table 2. For all medically attended LRTI (RSV, non-RSV, protocoldefined, non-protocol defined), the total number of events for each subject and the percentage of each outcome will be summarized by treatment group on three time-intervals: through 150 days post 1st dose (on the ITT population), after 150 days post 1st dose (on the ITT population with Day 151 visit), through 360 days post 1st dose (on ITT population). In addition, a listing that provides relevant information for subjects with more than one medically attended LRTI event throughout the study will be generated. The listing contains the following information: Age at randomization, Hemisphere, Total number of events, Days post 1st dose, AE verbatim term, Date of AE onset/stop, Days from previous event, Visit setting, Protocol-defined (Y/N), RSV (Y/N), and RSV subtype (when applicable). A similar listing for subjects with more than one medically attended RSV LRTI event (regardless protocol-defined or not) will also be presented.

Table 2 Definition for New Onset of Events

Event	Description	
New onset medically attended RSV LRTI	A new onset medically attended RSV LRTI will be defined as an adverse event (AE) (for which at least one healthcare visit is associated with RSV LRTI) and occurs at least 14 days (and similarly using 30 days) after the resolution date of the previous AE for a medically attended RSV LRTI.	
New onset RSV LRTI hospitalization	A new onset medically attended RSV LRTI hospitalization will be defined as an AE (for which at least one hospitalization is associated with RSV LRTI) and occurs at least 14 days (and similarly using 30 days) after the resolution date of the previous AE for a medically attended RSV LRTI hospitalization.	
New onset medically attended RSV outpatient LRTI	A new onset medically attended RSV outpatient LRTI will be defined as an AE (for which at least one healthcare outpatient visit is associated with RSV LRTI) and occurs at least 14 days (and similarly using 30 days) after the resolution date of the previous AE for a medically attended RSV outpatient LRTI.	
New onset medically attended LRTI	A new onset medically attended LRTI will be defined as an AE of LRTI that occurs after the resolution date of the previous AE for a medically attended LRTI.	
New onset LRTI hospitalization	A new onset medically attended LRTI hospitalization will be defined as an AE (with at least one hospitalization associated with LRTI) that occurs after the resolution date of the previous AE for a medically attended LRTI hospitalization.	
New onset medically attended outpatient LRTI	A new onset medically attended outpatient LRTI will be defined as an AE (with at least one outpatient healthcare visit associated with LRTI) that occurs after the resolution date of the previous AE for a medically attended outpatient LRTI.	

AEs associated with all medically attended LRTI will be summarized overall, as well as categorized by the Medical Dictionary for Regulatory Activities (MedDRA) system organ class (SOC) and preferred term (PT). Summaries will be presented through 150 days, after 150 days, and through 360 days post 1st dose on the following populations: ITT, ITT with Day 151 visit, ITT, respectively.

